### **Summary:**

Chronic Pelvic Pain is a debilitating, multimodal disease with several contributing organ systems. As a result, adequate treatment of this disease requires multimodal pain therapy from a team of experts. Other multimodal pain bundles (such as ERAS in the perioperative setting) have been shown to be superior to any bundle component being used as a monotherapy. This study will assess patient response to a bundled-care approach to CPP both pre-and post intervention as well as compared to a site randomized “usual care” cohort.

### **Background/Rationale:**

Chronic pelvic pain (CPP) is a common, debilitating condition experienced by up to 26% of adult women, costing billions in direct healthcare costs and indirect productivity costs annually. CPP deeply affects women’s quality of life, including everyday functioning and intimacy. Though there is no consensus definition, it is generally defined as generally defined as non-cyclic pain perceived to be in the pelvic area that has persisted for three to six months or longer and is unrelated to pregnancy.

CPP is challenging to treat, as it typically is insidious and the pathophysiology involves overlap of several related neuroimmune disorders affecting a litany of pelvic end-organs, including the muscles of the pelvic floor/vagina, bladder, colon and rectum, as well as the bony pelvis and hip girdle. It is closely tied to conditions such as endometriosis, interstitial cystitis, and irritable bowel syndrome. It is also exacerbated by emotional, physical, and sexual trauma, and worsened by central sensitization by depression, anxiety, and substance abuse. Systemic pain conditions such as fibromyalgia and autoimmune diseases are commonly found in women with CPP. On average, women who experience CPP may have a 4-11 year delay in diagnosis and seek the consultation of multiple providers before they find a pelvic pain specialist with an understanding of the complex mechanisms that perpetuate pain.

Most women who present to CPP specialists have tried several monotherapies, including combined oral contraceptive pills, repeated doses of antibiotics, over the counter pain medications, and other psychoactive medications, many of which are part of chronic pain treatment algorithms. In women with interstitial cystitis, the 2015 and 2022 AUA IC/PBS guidelines for treatment remain algorithmic and stepwise, despite literature that suggests that sequential monotherapy is a poor strategy. Only recently have studies emerged showing that multidisciplinary clinics for female CPP are both clinically effective and cost effective and may improve uptake/compliance with physical therapy and mental health recommendations, which are poor in this cohort. While many studies have been done over decades of research on the various mechanistic cascades that perpetuate chronic pain, there has been little to no research done on a “bundled” approach to chronic pain. Care bundles are a set of three to five evidence-informed practices performed collectively and reliably to improve the quality of care.

This approach takes advantage of treating pain as a polymodal affliction, requiring treatment for central-neural sensitization pathways, emotional trauma, infectious/microbiome modulation, immune factors, surgical interventions, and physical therapy for end-organ rehabilitation. Similar studies on “bundled care” have been done for infection control and show that no single intervention reduces infection in a significant way, but collectively each component of the care bundle provides dramatic improvements. From an acute and postoperative pain standpoint, Enhanced Recovery After Surgery (ERAS) bundles have shown remarkable effectiveness for improving postoperative recovery despite studies that fail to show effectiveness for components of the bundle as monotherapies. However a similar bundled, multimodal approach has not been formally presented or studied for CPP.

### **Objectives:**

The goals of this research program are to evaluate the patient-reported outcomes of a multimodal care bundle for patients presenting to a multidisciplinary CPP clinic compared to “usual care” in an FPMRS or Urology clinic.

### **Primary Aim:**

To compare pre and post intervention self-evaluation of pain and function scores in women with chronic pain syndromes with a primary finding of urinary/bladder pain symptoms **and/OR levator** spasm who undergo multi-disciplinary, bundled care compared with usual care in a FPMRS or Urology clinic setting.

### **Secondary Aims:**

- a) To identify and phenotype “non-responders” to a bundled approach to IC/PBS/ CPP.

**Hypothesis:** We hypothesize that a bundled, multidisciplinary care approach will significantly improve patient scores on validated outcomes questionnaires compared to usual care.

### **Methods:**

All treatment plans, medications, and procedures recommended for patients involved in this study are within the current standards of care for IC/PBS/ CPP, regardless of treatment arm and are known to be safe interventions.

**Study Design:** Single center, randomized pre-post intervention/prospective cohort study of usual FPMRS care vs. multimodal, multidisciplinary care bundle (MMCB).

STROBE guidelines were utilized.

**Setting:** Patients will be recruited from an outpatient Female Pelvic Medicine and Reconstructive Surgery (FPMRS) clinic. They will subsequently be randomized to a

Multidisciplinary CPP clinic at an alternate site vs. continuing usual outpatient care in FPMRS as above.

**Study Population/Participants:** Eligible participants include self-referred women 18 years and older with a clinical diagnosis of IC/PBS (based on history and symptoms) who scored 6 points or greater on the problem OR symptom index of the O’Leary Sant Questionnaire. Every attempt will be made to fulfill a representation quotient.

**Inclusion Criteria:** Female patient 18 years of age or older, clinical diagnosis of CPP and IC/PBS, scoring 6 points or higher on O’Leary Sant Questionnaire **(IC/PBS arm) OR levator spasm diagnosed by an FPMRS specialist.**

**Exclusion Criteria:** active pelvic or bladder infection within past 2 weeks, contraindications to medications or intervention therapeutics, inability to speak or read English; pelvic floor interventional procedure including bladder instillations 4 weeks prior to study recruitment, **meets criteria for diagnostic laparoscopy (dysmenorrhea, uterine pain, cyclic pelvic pain, dyspareunia, GI symptoms)**

Note: patients are not excluded for currently taking any medication on the treatment list. Patients can be treated for UTI during the study period.

**Randomization:** If patients meet inclusion criteria and agree to participate, they will be randomized by RedCap either to remain in “usual” care in the FPMRS or Urology clinic or transition their care to the multidisciplinary CPP clinic at the UPMC Lemieux Center.

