#### **Definition of outcome measure and method of ascertainment:**

Data collected at baseline, 6 weeks, 12 weeks, 6 months, 1 year

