#### Primary Outcome

--O'Leary Sant Questionnaire (OLS), comprised of Interstitial Cystitis Symptom Index (ICSI) and Problem Index (ICPI), at 12 weeks from baseline  
MCID: 4 points for ICSI

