#### Secondary Outcomes

- NRS Scale
- McGill Pain Questionnaire, Short Form^39
- Pain Disability Index
- Pelvic Pain and Urgency/Frequency Questionnaire (PUF)
- Pelvic Floor Distress Inventory (PFDI)-20^42
  - MCID: 45 points (15%)
- Female Sexual Function Index (FSFI)
  - MCID: 2.1 points
- Pain Catastrophizing Scale (PCS)
- Patient Global Impression of Improvement (PGI-I)

- 1) Healthcare utilization defined as number of additional encounters for chronic pelvic and bladder pain diagnosis outside of the defined study period
  - a. Phone calls
  - b. Office visits
  - c. ER visits
  - d. Procedures

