**7) Pyridium 100-300mg/day**

8) Microbiome: Methenamine

9) Vaginal estrogen

At least once within 12 weeks of initial visit:

10) Intravesical evaluation: Cystoscopy to evaluate for hunner ulcers or variant (treat with Kenalog injection alone if Hunner ulcers or variant with or without hydrodistention if no hunner ulcers)

11) Bladder instillations x 6 weeks (lidocaine, heparin, sodium bicarb, available glucocorticoid (dexamethasone, etc), gentamicin)

-Invasive interventions to be repeated as needed per patient.

Data will be stored and managed in a RedCap database

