### **Ethical Concerns:**

Pain patients are a vulnerable population.

**Strengths/Weaknesses;** patients cannot be blindly randomized, interventions are evidence-based but not being studied separately. There are likely differing phenotypes of pain patients (endometriosis vs. infectious vs. trauma) making for a heterogeneous population.

**Timeline:** 12 month enrollment and 12 month follow up.

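### The outcome list contains no harms in either arm, so the trial could not describe the bundle's harms beside its benefit

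*Combined protocol and SAP*

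**What the plan says.** The opening of Methods says that the treatments "are within the current standards of care for IC/PBS/ CPP, regardless of treatment arm and are known to be safe interventions". The subject of that sentence covers whole plans of treatment as well as single drugs and procedures. Under Background/Rationale the plan says: "However a similar bundled, multimodal approach has not been formally presented or studied for CPP". Under Strengths/Weaknesses it adds that the "interventions are evidence-based but not being studied separately".

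The Intervention section numbers 11 components. They include several drugs, a nerve block, cystoscopy and a six-week course of bladder instillations, and the list closes with "Invasive interventions to be repeated as needed per patient". A heading at item 6 limits some components to women with IC/PBS. It is not clear whether it governs item 6 alone or the items after it as well.

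The assessment schedule is "Data collected at baseline, 6 weeks, 12 weeks, 6 months, 1 year". The primary outcome is the O'Leary-Sant questionnaire (OLS), "comprised of Interstitial Cystitis Symptom Index (ICSI) and Problem Index (ICPI), at 12 weeks from baseline". The secondary outcomes are eight questionnaires or scales, plus healthcare utilization (phone calls, office visits, ER visits, procedures), defined as the "number of additional encounters for chronic pelvic and bladder pain diagnosis outside of the defined study period".

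**The concern.** The bundle adds drugs and repeatable invasive procedures to a patient's care, and the plan itself describes the combined approach as not formally studied in this condition. Nothing in the outcome list would show what that costs patients in side effects, infections or complications.

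The plan foresees such events without recording them. Methods allows UTIs to be treated during the study, and the baseline data include a history of recurrent UTI, but no on-study UTI is listed. The bladder-medication item makes dose increases depend on tolerance, yet intolerance is not captured.

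If the bundle does better on OLS, the report could state the benefit but could not set harms by randomised arm beside it. Harms not asked about at each visit cannot be fully recovered afterwards.

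**Working it through.** **Step 1: what a trial run as written would return.** The places that could hold a harm are set side by side.

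| Section | What is collected | Does it capture harm? |
|---|---|---|
| Demographic Data | Baseline characteristics and history | No, baseline only |
| Primary Outcome | OLS at 12 weeks | No, symptom score |
| Secondary Outcomes, scales | Eight questionnaires, including the global impression of improvement (PGI-I) | PGI-I can show that a woman feels worse, but not which harm or from what |
| Secondary Outcomes, utilization | Calls, visits, ER visits, procedures | Only for pain diagnoses, and worded as falling outside the study period |
| Intervention | Components given | No complication or intolerance record |
| Ethical Concerns | Notes that patients are vulnerable | No monitoring described |

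The utilization item might be meant to count contacts beyond the scheduled study visits. Even so, it is limited to pain diagnoses and would miss a drug side effect or an infection coded as such.

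**Step 2: the plan's figure.** The plan gives no figure for harms. Its one computed design figure is 40 per group. From the stated difference of 6, SD of 5.6, two-sided alpha of 0.05 and 90% power, a t-test needs 20 per group, and 20 / 0.80 = 25 after dropout, so 40 is not reproduced. That is a separate matter. Here 40 is taken as the enrolment target, and with 20% dropout 40 × 0.80 = 32 are followed per arm.

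**Step 3: what recording would show in one arm.** The rates of 5% and 10% are assumptions for illustration. P(at least one event) = 1 − (1 − p)^n. The exact two-sided 95% upper limit with zero events is 1 − 0.025^(1/n).

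| | n = 32 | n = 40 |
|---|---|---|
| p = 5% | 1 − 0.95^32 = 0.806 | 1 − 0.95^40 = 0.871 |
| p = 10% | 1 − 0.90^32 = 0.966 | 1 − 0.90^40 = 0.985 |
| Upper limit, zero events | 1 − 0.025^(1/32) = 0.109 | 1 − 0.025^(1/40) = 0.088 |

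For a component given only to women with IC/PBS, n is smaller. The plan does not give the mix. If half of the 32 were exposed (an assumption), the 5% figure would fall to 1 − 0.95^16 = 0.56, and the zero-event limit would rise to 1 − 0.025^(1/16) = 0.206.

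**Step 4: what recording would show between arms.** Take assumed rates of 5% and 15%, whose mean is 10%. Power is Φ[(0.10 − 1.96 × √(2 × 0.10 × 0.90 / n)) / √((0.05 × 0.95 + 0.15 × 0.85) / n)].

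- n = 40: Φ[(0.10 − 1.96 × 0.0671) / 0.0661] = Φ(−0.476) = 0.32.
- n = 32: Φ[(0.10 − 1.96 × 0.0750) / 0.0740] = Φ(−0.636) = 0.26.

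Only a large difference would be detected reliably: for 5% against 30%, the same formula gives 85% with 40 per arm and 76% with 32.

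**The case against.** The strongest case against the point is one of scope. The stated aims concern patient-reported outcomes and non-responders. Every treatment is described as standard care, and women with contraindications are excluded. No stated aim or primary analysis fails without a harms outcome. That is true, and it limits the severity of the point. It does not close the gap, because exclusion at entry does not measure what happens after treatment starts.

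Four stronger readings are tempting, and the documents do not support them.

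- A reader might infer that harms were left out because the treatments are called safe. Methods asserts safety but gives no reason for the choice of outcomes.
- A reader might infer that the safety statement concerns single components only. It also covers plans of treatment. The tension is therefore between that broad assertion and the Background, which says that the bundled approach lacks formal study.
- A reader might infer that nothing like the bundle has ever been studied. The Background's statement is about a formally presented or studied bundle in chronic pelvic pain, and the same section cites studies of multidisciplinary clinics with favourable results.
- A reader might infer that there is no safety reporting at all. Consent and other pages are not in the text reviewed, so institutional event reporting cannot be ruled out. It would not in itself add a harms outcome compared by arm to the listed measures.

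Two statistical objections also stand: the between-arm comparison would be weak, and self-reported events may be ascertained differently by arm because treatment is unblinded.

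**Conclusion.** The point holds as an omission from the listed outcomes. Neither arm has a prespecified harms measure, and utilization and PGI-I do not fill the gap. The OLS comparison is unaffected, and nothing here shows that the bundle is unsafe. What is lost is a description of its harms by arm. The change should be made, but the primary analysis does not depend on it.

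With 32 followed per arm, recording would very probably reveal harms at a true rate of 10% (97%) and usually those at 5% (81%). Zero events would leave rates up to 10.9% compatible with the data. With all 40 followed, these become 98.5%, 87% and 8.8%. The figures rest on the assumed rates, on the plan's 20% dropout and, for any given component, on all the women counted having received it. They support description and not a test between arms.

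**What to change.** 1. Add a secondary harms outcome under Definition of outcome measure and Secondary Outcomes. Use one structured REDCap form with the same questions in both arms at 6 weeks, 12 weeks, 6 months and 1 year. It should cover adverse events, culture-proven UTI, procedure complications and drugs stopped for side effects since the last form. It should also record which procedures were received, so that denominators are known.
2. Report counts and risk differences by randomised arm with 95% confidence intervals, labelled descriptive. Report procedure harms also among women who received the procedure, and state that this is not a randomised comparison.
3. Reword the safety statement in Methods, including its reference to plans of treatment, so that it does not extend to the combined bundle.

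The cost is one form at time points that are already scheduled, and budgeted with patient payments, in a database already in use. It takes a few minutes of participant and coordinator time per visit. Identical questions reduce the difference in ascertainment between unblinded arms but do not remove it, and the report should say so. No treatment or clinical rule changes.

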#### **Definition of outcome measure and method of ascertainment:**

Data collected at baseline, 6 weeks, 12 weeks, 6 months, 1 year

#### Demographic Data

Age

Self-Identified Race

Height/Weight/BMI

Menopausal Status

Currently using hormones

-Oral contraceptives (list)

-Intrauterine device (list)

-Hormone replacement

-Hormone-containing topical cream or ointment

-Other (list)

Other pain conditions

Fibromyalgia

Migraine

Endometriosis

Prior treatments for chronic pelvic or bladder pain (list)

Number of vaginal deliveries

Number of cesarean deliveries

Prior treatments for pelvic bladder pain

- Medications
- Pelvic floor physical therapy
- Cystoscopy with hydrodistention
- Other cystoscopy
- Pelvic floor injections
- History of culture-proven recurrent UTIs (yes/no)
  - Give details
- History of psychiatric diagnoses
  - Depression
  - Anxiety
  - Bipolar disorder
  - PTSD
  - Psychosis/Hallucinations
- Other (list)
- History of physical or sexual abuse (yes/no)

#### Primary Outcome

--O'Leary Sant Questionnaire (OLS), comprised of Interstitial Cystitis Symptom Index (ICSI) and Problem Index (ICPI), at 12 weeks from baseline  
MCID: 4 points for ICSI

#### Secondary Outcomes

- NRS Scale
- McGill Pain Questionnaire, Short Form^39
- Pain Disability Index
- Pelvic Pain and Urgency/Frequency Questionnaire (PUF)
- Pelvic Floor Distress Inventory (PFDI)-20^42
  - MCID: 45 points (15%)
- Female Sexual Function Index (FSFI)
  - MCID: 2.1 points
- Pain Catastrophizing Scale (PCS)
- Patient Global Impression of Improvement (PGI-I)

- 1) Healthcare utilization defined as number of additional encounters for chronic pelvic and bladder pain diagnosis outside of the defined study period
  - a. Phone calls
  - b. Office visits
  - c. ER visits
  - d. Procedures

#### **Intervention:**

##### Components of MMCB (all)

- 1) MD Evaluation (FPMRS or Urology)
- 2) Pelvic floor physical therapy (PFPT)

3) Behavioral health consult if patient does not have established behavioral/psychiatric care →with appropriate psychiatric referrals/treatments

4) Central sensitization/neurogenic pain:

Amitriptyline 10-50mg 

Or Gabapentin (doses range from 100mg po tid to 600mg po tid)

**5) Pudendal/Levator and/or Obturator internus nerve block (120mg Kenalog and 0.25% Marcaine, total 23-33cc) in office or under anesthesia**

**6) Urinary symptoms IC/PBS ONLY**

Spasm: OAB medication chosen based on patient characteristics/insurance, dose may be increased as tolerated (anticholinergic vs. b-agonist)

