**Demographic data:**

Age, self-identified race, BMI, menopausal status, past medical history, past surgical history, psychiatric history, tobacco, sexual assault/abuse history, history of prior interventions for their chronic pain condition, internal vs. external referral

**Study Size/Power Calculation:** based on the primary outcome, the primary outcomes is defined as the change in the total OLS score from baseline to 12 weeks compared between the groups. Based on previous studies, patients with IC/BPS have a baseline OLS score following standard medical treatment of  $24 \pm 5.6$  190 points. . A 4.03-point

decrease from baseline on the OLS-ICSI corresponds with at least a 50% perceived improvement in symptoms, we have chosen to use 6 points, to represent 75% improvement. We desired 90% power to detect a 6-point or larger difference in the mean score change between the groups with a 2-sided t-test at a significance level of  $\alpha=0.05$ . Accounting for 20% dropout, the target sample size was 40 for each group (80 total).

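### Women can probably enter on levator spasm alone, yet the O'Leary-Sant primary outcome, the sample size and the randomisation take no account of entry route

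*Combined protocol and SAP*

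**What the plan says.** **Entry.** The Primary Aim covers women with urinary or bladder pain symptoms "and/OR levator" spasm. The Inclusion Criteria in Methods first name a clinical diagnosis of CPP and IC/PBS with an OLS score of at least 6, then continue "IC/PBS arm) OR levator spasm diagnosed by an FPMRS specialist". No OLS minimum is attached to the levator route. The Study Population paragraph is narrower: "Eligible participants include self-referred women 18 years and older with a clinical diagnosis of IC/PBS".

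**Bundle.** In the Intervention section, items 1 to 5 (physician evaluation, pelvic floor physical therapy, behavioural health, amitriptyline or gabapentin, nerve block) carry no restriction by diagnosis. Item 6, medication for overactive bladder, is headed "6) Urinary symptoms IC/PBS ONLY". Items 7 to 11, including cystoscopy and bladder instillations, follow under their own numbers.

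**Outcome and size.** The primary outcome is OLS, "comprised of Interstitial Cystitis Symptom Index (ICSI) and Problem Index (ICPI), at 12 weeks from baseline". The Study Size/Power Calculation defines it as change in total score. It starts from the statement that "patients with IC/BPS have a baseline OLS score following standard medical treatment of" 24 ± 5.6, and continues: "We desired 90% power to detect a 6-point or larger difference in the mean score change between the groups". It allows 20% dropout and arrives at 40 per group.

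**Allocation.** Women who qualify and agree to take part: "they will be randomized by RedCap". No stratification factor is given. The plan states no expected share of levator-only women and no analysis by entry route.

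**The concern.** Eligibility and treatment differ by diagnosis, but the endpoint, the effect size and the allocation do not. A woman who enters on levator spasm alone may start with a low score on an interstitial cystitis instrument, does not receive at least item 6, and still counts fully in the OLS comparison. The 6-point target was set with IC/BPS patients in mind.

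Randomisation still protects the comparison from bias. What is at stake is power and meaning. A small or null pooled difference could reflect how many levator-only women happened to enrol and not a failure of the bundle in IC/PBS, and the plan sets up no prespecified way to tell the two apart. In a trial of 80 without stratification, the two arms can also differ by chance in their share of levator-only women.

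**Working it through.** **Inputs from the Study Size/Power Calculation:** two-sided t-test, α = 0.05, difference 6 points, SD 5.6 (printed for the score level; no SD of change is given), 40 per arm, 20% dropout, so 40 × 0.8 = 32 evaluable per arm.

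**The plan's own figure.** Normal approximation: n = 2(1.96 + 1.28)² × 5.6² / 6² = 18.3, so 19 per arm, or 20 with the exact t-test. Dividing by 0.8 gives 24 or 25 per arm, not 40. Working back, 32 evaluable per arm give 90% power at an SD of about 7.3, which the plan does not print. Both SDs are therefore carried forward.

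**Dilution.** Let p be the levator-only share and e the between-arm OLS gain in those women. The expected pooled difference is

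Δ = 6(1 − p) + e·p.

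The noncentrality is Δ / (SD × √(2/32)) = Δ / (0.25 × SD), with 62 degrees of freedom and critical value 2.00. For example, with p = 25% and e = 0, Δ = 6 × 0.75 = 4.5. At SD 5.6 the noncentrality is 4.5 / 1.4 = 3.21 and power is 89%.

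| p | e | Δ | Power, SD 5.6 | Power, SD 7.3 |
|---|---|---|---|---|
| 0 | – | 6.0 | 99% | 90% |
| 10% | 0 | 5.4 | 97% | 83% |
| 10% | 2 | 5.6 | 98% | 86% |
| 25% | 0 | 4.5 | 89% | 68% |
| 25% | 2 | 5.0 | 94% | 77% |
| 25% | 3 | 5.25 | 96% | 81% |
| 50% | 0 | 3.0 | 56% | 37% |
| 50% | 2 | 4.0 | 80% | 58% |
| 50% | 3 | 4.5 | 89% | 68% |

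**Sensitivity to the common SD (e = 0).** Adding the extra variance from mixing responders and non-responders in the bundle arm lowers power at 25% and 50% shares to 85% and 51% (SD 5.6), or 66% and 34% (SD about 7.3). If levator-only women vary half as much, power at SD 7.3 is 74% and 49%.

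**Would restricting the primary set be better?** Dropping levator-only women restores the 6 points but shrinks n by the factor (1 − p). The two approaches break even where 6(1 − p) + e·p = 6√(1 − p):

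- p = 25%: e = (5.196 − 4.5) / 0.25 = 2.78
- p = 50%: e = (4.243 − 3.0) / 0.50 = 2.49

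At p = 20%, the IC/PBS entrants number 64, or 64 × 0.8 / 2 = 25.6 evaluable per arm. Power is then 96% (SD 5.6) or 82% (SD 7.3). Pooled power is 92% or 74% with e = 0, and 97% or 83% with e = 3. Restriction wins only when the levator-only gain is below about 2.5 to 2.8 points.

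**The case against.** **The steep losses are a corner case.** A 25–50% share, zero gain and an SD of 7.3 are not in the documents. At the only printed SD, a 25% share with zero gain still leaves 89%, about what was planned. This stands, and the figures are an illustration only.

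**Zero gain is hard to square with the bundle.** Items 1 to 5 go to everyone, and the protocol supports two of them, amitriptyline and pelvic floor physical therapy, with trials in interstitial cystitis/painful bladder syndrome. This also stands, and is why gains of 2 and 3 points are shown. Against it, a levator-only woman with a low baseline OLS has little room to improve.

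**The premise depends on ambiguous wording.** The Inclusion Criteria can be read as requiring IC/PBS of everyone, in which case p = 0 and there is no dilution. The Study Population sentence supports that reading. The Primary Aim, the label for an IC/PBS arm and the restriction on item 6 point the other way, since that restriction would have little purpose if every woman had IC/PBS. The levator-alone reading is the likelier one but is not certain.

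**Two stronger readings are not supported.** A reader might infer that levator-only women receive none of the bladder treatment. The restriction is printed on item 6 alone, and nothing shows that it reaches items 7 to 11. A reader might also infer that the trial is underpowered. The documents do not establish that, because they give neither the mix nor the gain.

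**The plan already offers some help.** Baseline OLS is collected, non-responders are to be phenotyped, and heterogeneity is acknowledged. None of this is a prespecified comparison by entry route.

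**Conclusion.** The mismatch is in the text, on the likelier reading of eligibility: the plan allows two entry routes, while its primary outcome, sample size and allocation are built for one. Its effect on power is conditional. With a 10% share, power stays at 97% or more (SD 5.6) or 83% or more (SD 7.3). At SD 5.6 it is still 89% or more at a 25% share. A material loss needs either a share nearer 50% with little gain, or an SD near 7.3. The firmer cost is interpretive: as written, a weak pooled result could not be attributed by any planned analysis to case mix or to the bundle. That is worth correcting because the correction is cheap, not because a power failure has been shown.

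**What to change.** 1. Record entry route in REDCap before randomisation: IC/PBS criterion met, with or without levator spasm; or levator spasm alone.
2. Stratify allocation by it.
3. Keep all randomised women in the primary analysis, with entry route and baseline OLS as covariates.
4. Prespecify the 12-week OLS comparison in IC/PBS entrants as the key supporting analysis, and report NRS pain, already a secondary outcome, descriptively in levator-only women.

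Adjustment does not undo the dilution. Item 4 is what lets the trial separate case mix from bundle failure.

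The cost is one extra REDCap field and one extra analysis. Precision in a small levator-only stratum will be low: 16 such women would leave about 6 evaluable per arm and roughly 25% power for a 0.8 SD effect, which is why that report should be descriptive.

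Recruiting 80 IC/PBS women, capping levator-only entry or restricting the primary set are not required. The first means 80/(1 − p) enrolled, or 107 at p = 25% and 160 at 50%. Restricting the primary set leaves out women whom the Primary Aim names, and gains power only below the break-even above. These trade-offs are for the investigators.
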